STATISTICS Primary analysis plan	
Statistical Methods: A detailed statistical analysis report will be written that will describe all analyses, tables, figures, and data listings generated for this study. All analyses will be performed using SAS ® (SAS Institute, Cary, NC, USA).
 
Analysis Populations: All analyses will be performed using an intent-to-treat (ITT) population, which is defined as all randomized subjects. Subjects who are discontinued from the study temporarily or permanently will remain in the analyses population according to ITT.
 
Demographic and Baseline Characteristics: Summary statistics will be calculated for demographic and baseline characteristics (age, sex, genotype, diabetic status, FEV₁ % predicted) time to therapeutic dosing for colistin versus tobramycin, number of therapy interruptions between study arms, and total number of IV antibiotic doses. Study medications and exposure to study drug data will be summarized in contingency tables.
 
Summary statistics and changes from

admission visit to end of treatment will be presented for FEV₁ % predicted and questionnaires, on an intent-to-treat basis, including all subjects receiving at least three days of colistin or tobramycin, and at least one efficacy assessment.

Analysis of Primary Endpoints:

Efficacy analysis: We will perform equivalence testing to show similarity of colistin treatments, as well as for colistin vs tobramycin treatments. For both comparisons, confidence intervals for difference in FEV₁ changes from pre to post treatment time points will be constructed, and equivalence tests to within 5% will be performed. Times to next pulmonary exacerbation and occurrence of neurotoxicity between standard colistin and PK-adjusted colistin will be analyzed using the Kaplan-Meier method. Subsequent pulmonary exacerbations in the ensuing year for all enrolled subjects, as well as antimicrobial resistance to tobramycin and colistin before and after treatment, will be summarized. Unless otherwise noted, 2-sided tests will be used with $\alpha = 0.05$.

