Pilot study of PK parameters in an adult CF cohort with APE: We assayed steady-state pharmacokinetic and pharmacodynamic properties of intravenous colistin in CF subjects >18 years old admitted for APE treatment, during the first week of admission. The primary objective of the study was to determine PK parameters, specifically clearance (CL), volume of distribution (VD), area under the curve (AUC), and maximal concentrations (Cmax). A total of 16 CF subjects were evaluated. All subjects received IV colistin on a standard dosing schedule, in conjunction with other anti-Pseudomonal antibiotic agents, dosed three times daily. Patient characteristics are depicted in Table 1. Steady state plasma concentrations were obtained after \geq 2 days of therapy during week 1 of admission, and subjects underwent phlebotomy at 0, 0.5, 1, 2, 4, and 6 hours after administration. Peak, midpoint, and trough colistin A and B concentrations (active drug) were measured utilizing liquid chromatography-mass spectrometry (LC-MS) technology^{21,22}. As seen in Table 1, the mean study age of 32 is older than mean ages in prior studies of IV colistin in CF subjects^{19,20}. Mean FEV₁ % predicted was 40% predicted at onset of exacerbation, demonstrating that the drug can be given safely with severe airflow limitation. There were no reported side effects of chest tightness that would limit its use. Two subjects experienced SCr rises of \geq 0.3 mg/dL, necessitating discontinuation of drug. Mean colistin dosing was 3.42 mg/kg/d over 15 days. A PK analysis of

Table 1: Characteristics of colistin PK pilot study subjects

No. of subjects	16
Gender- no. (% female)	8 (50)
Age (mean \pm SD years)	32 \pm 13
Sputum culture	
Pseudomonas aeruginosa only	8 (50)
Pseudomonas aeruginosa, Staphylococcus aureus, and/or other GNR	8 (50)
Concomitant systemic antibiotic therapy- no. (%)	
β -lactam, carbapenem, monobactam, or quinolone	16 (100)
vancomycin or linezolid	5 (31)
FEV ₁ (mean \pm SD % predicted)	40 \pm 15
Mean dose colistin- mg/kg/d (mean \pm SD)	3.42 \pm 0.6
Mean duration of therapy-days (mean \pm SD)	15 \pm 9
Baseline SCr- mg/dL (mean \pm SD)	.77 \pm .27
Number with AKI (% with $>$ 0.3 mg/dL increase in SCr)	2 (13)
SCr- serum creatinine	
AKI- acute kidney injury	

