Standard tobramycin arm: Subjects receive IV tobramycin 8-10 mg/kg/day (X-gen Pharmaceuticals) with once daily dosing for 14 days. Peaks and troughs are drawn with the second dose of tobramycin, and the drug is infused over 30 minutes. Dose adjustment will occur to achieve non-detectable troughs and peaks 20-30 mg/dL². Tobramycin concentrations are assessed once weekly during each week of APE treatment.

8.4.3 Dose modification: Subjects active in the study who experience moderate to severe toxicity will undergo dose adjustments as follows. If clinical providers and site investigators believe that it is appropriate to have the subject continue in the study, this will be allowed. If study drug is discontinued, the data acquired prior to its discontinuation will be utilized in the analysis.

1. Tobramycin will be discontinued if ototoxicity occurs (patient complains of ringing in ears and/or hearing loss).
2. Tobramycin will be held with increases of creatinine >0.3 mg/dL. If creatinine increases are not reversible, the drug is discontinued. If they are reversible, the drug may be resumed at lower dosing or longer intervals, at the discretion of the physician and the clinical pharmacist in joint consultation.
3. Colistin will be discontinued for serious episodes of neurotoxicity, such as debilitating headache, seizure, and neuromuscular weakness.
4. Colistin will be held for one dose and then resumed at a lower dose if creatinine rises \geq 0.3 mg/dL from baseline. If creatinine fails to recover or continues to rise, the drug will be discontinued. Patients who do not undergo PK measurements are maintained at the highest dose achievable (between 3-5 mg/kg/day) without renal insufficiency (< 0.3 mg/dL increase in serum creatinine).

8.4.4 Study drug preparation, handling and dispensing: Appropriately trained pharmacy personnel and nursing staff are responsible for the administration of medications. Medications are dispensed and labeled in accordance with federal and local state Board of Pharmacy regulations.

8.4.5 Administration instructions: Instruction of hours of administration, dose, and duration of administration will be transmitted from the National Jewish Health | Saint Joseph Hospital inpatient pharmacists to CF pulmonary floor nursing staff. Drugs will be administered through indwelling peripherally inserted central catheters (PICC) or indwelling ports.

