12.1 Early Discontinuation of the Study Treatment

A subject may be discontinued from study treatment at any time if the subject, the investigator, or the Sponsor feels that it is not in the subject's best interest to continue. The following is a list of possible reasons for early discontinuation of study treatment:

- Subject or subject's legal representative decision
- Adverse event
- Protocol violation
- Death

If a subject is discontinued from treatment due to an adverse event, the subject will be followed and treated by the Investigator until the abnormal parameter or symptom has resolved or stabilized.

All subjects who discontinue study treatment early will be evaluated for an early discontinuation of study treatment visit as soon as possible and then encouraged to complete all remaining scheduled visits and procedures.

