[name] will monitor the data collection for accuracy and quality for the study. Data will be collected from subject medical and research records and maintained in electronic Case Report Forms (eCRFs) using REDCap (Research Electronic Data Capture), a secure web-based application that supports data capture for research studies.

15. Statistical Methods and Considerations

15.1 General: Summary statistics will be calculated for demographic and baseline characteristics (age, sex, genotype, diabetic status, FEV₁ % predicted) time to therapeutic dosing for PK-adjusted colistin versus tobramycin, number of therapy interruptions between study arms, and total number of IV antibiotic doses. Study medications and exposure to study drug data will be summarized in contingency tables. Summary statistics and changes from admission visit to end of treatment will be presented for FEV₁ % predicted and questionnaire results, on an intent-to-treat basis, including all subjects receiving at least three days of colistin or tobramycin, and at least one efficacy assessment. Subjects will be enrolled once.

15.2 Efficacy analysis: We will perform equivalence testing to show similarity of colistin treatments, as well as for colistin vs tobramycin treatments. For both comparisons, confidence intervals for difference in FEV₁ changes from pre to post treatment time points will be constructed, and equivalence tests to within 5% will be performed. These will be derived from linear mixed models fitted for FEV₁ that include a random intercept for subjects to account for repeated measures, and the following covariates: age, other medication, admits in the previous year, and diabetes. Nested random terms will be included in the model to account for repeated measures – one for subject and one for visit within subject. CFQ-R domain scores will be analyzed in a similar fashion. Times to next pulmonary exacerbation and occurrence of neurotoxicity between standard colistin and PK-adjusted colistin will be analyzed using the Kaplan-Meier method. Subsequent pulmonary exacerbations in the ensuing year for all enrolled subjects, as well as antimicrobial resistance to tobramycin and colistin before and after treatment, will be summarized. Unless otherwise noted, 2-sided tests will be used with $\alpha = 0.05$.

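### The FEV1 equivalence test is planned in all randomized subjects with no supporting on-regimen analysis, although ITT is not reliably conservative for equivalence

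*Combined protocol and SAP*

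**What the plan says.** **Test.** Section 15.2, like the synopsis, plans confidence intervals for the difference in FEV1 change and says that "equivalence tests to within 5% will be performed". This covers the two colistin regimens and colistin against tobramycin.

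**Population.** The synopsis (Statistics, Analysis Populations) says "All analyses will be performed using an intent-to-treat (ITT) population, which is defined as all randomized subjects", and then "Subjects who are discontinued from the study temporarily or permanently will remain in the analyses population according to ITT". The synopsis and section 15.1 also use the intent-to-treat label for summaries of FEV1 change in a narrower group, "including all subjects receiving at least three days of colistin or tobramycin, and at least one efficacy assessment".

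**Data after a stop.** Section 8.4.3 says "If study drug is discontinued, the data acquired prior to its discontinuation will be utilized in the analysis" and does not mention later data. Section 12.1 has subjects who stop early seen at a discontinuation visit and then "encouraged to complete all remaining scheduled visits and procedures".

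**Expected changes of exposure.** Section 8.4.3 provides for holding, lowering or stopping study drug after creatinine rises or toxicity. For tobramycin after a reversible rise, "the drug may be resumed at lower dosing or longer intervals". In the pilot (section 1.1), 2 of 16 subjects had creatinine rises "necessitating discontinuation of drug".

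**What is absent.** Neither the synopsis statistics section nor sections 15.1 to 15.4 contains a per-protocol set, an on-regimen set or a sensitivity analysis for the equivalence test.

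**The concern.** In a superiority trial, lost exposure usually works against the claim, so analysing everyone as randomized is the cautious choice. In an equivalence trial it can work for the claim: if subjects in the better arm lose the treatment that makes it better, the observed difference shrinks towards zero and fits inside the margin more easily.

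The protocol's own cohort makes this plausible for tobramycin versus colistin. Tobramycin had the larger FEV1 gain (12 versus 9 points) and also the higher AKI incidence (19% versus 12%), so it would lose more exposure under section 8.4.3. For standard versus PK-adjusted colistin, the documents give neither differential stopping rates nor an expected FEV1 difference, so the effect could go either way.

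At stake is how a finding of similarity is read. With a single analysis set, nobody can tell whether the regimens perform alike or whether lost exposure has hidden a difference.

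**Working it through.** **1. Stated figure.** There is none to reproduce: the documents give no power, SD or sample size for the equivalence test. Section 15.4 justifies 30 per group on safety and concedes that FEV1 may be underpowered. The size of the possible bias was therefore computed directly.

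**2. Inputs from the documents.** 30 per arm (15.4, equal allocation assumed). Margin 5, read as ±5 percentage points of FEV1 % predicted because the endpoint is an absolute change in that unit; the text says only 5%. AKI incidence 12% and 19% (section 1.1).

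**3. Assumptions.**
- Two one-sided t-tests at 0.05 each (a 90% interval). Section 15.2 gives two-sided 0.05 without naming the interval level for equivalence.
- SD of FEV1 change. Two rough values can be backed out:
  - Section 15.4 mentions 90 per arm originally. For the 3-point difference at an assumed 80% power, two-sided 0.05: SD = 3 × √(90/2) / (1.96 + 0.84) ≈ 7.2.
  - The cohort reports 3 points with p = 0.006, so z ≈ 2.75 and SE = 3/2.75 ≈ 1.09. Splitting 465 admissions as 240:350 gives about 189 and 276, so SD = 1.09 / √(1/189 + 1/276) ≈ 11.6. This treats the p-value as an unadjusted comparison of independent admissions.
- Dilution, worst case: a share q of subjects contributes no between-arm difference, so the observed mean difference is 5 × (1 − q). For q = 12% this is 4.40; for q = 19% it is 4.05.

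**4. Formula, at SD 7.2.** SE = 7.2 × √(2/30) = 1.86. With 58 degrees of freedom t = 1.672, so the half-width is 3.11, and the estimate must lie within ±(5 − 3.11) = ±1.89. Holding the sample SD fixed:
- q = 0: Φ((1.89 − 5.00)/1.86) = Φ(−1.67) ≈ 4.7%
- q = 12%: Φ((1.89 − 4.40)/1.86) = Φ(−1.35) ≈ 8.8%
- q = 19%: Φ((1.89 − 4.05)/1.86) = Φ(−1.16) ≈ 12.3%

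The lower-limit term is negligible.

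**5. Results with the sample SD allowed to vary** (integrated over its chi-square distribution). Chance of declaring equivalence when the true on-regimen difference is 5 points:

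| SD | q = 0 | q = 12% | q = 19% | True difference 0, no dilution |
|---|---|---|---|---|
| 7.2 | 5.0% | 9.2% | 12.6% | 69% |
| 8 | 4.9% | 8.5% | 11.3% | 55% |
| 10 | 3.6% | 5.4% | 6.6% | 21% |
| 11.6 | 1.3% | 1.8% | 2.1% | 5% |

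If only half the effect is lost in 12% of subjects (q = 6%), the figure at SD 7.2 is 6.9%. With a 95% interval at SD 7.2, the rates for q = 0, 12% and 19% are 2.5%, 4.9% and 7.0%.

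**6. Cost of a smaller set.** At SD 7.2 and a true difference of 0, the chance of declaring equivalence falls from 69% with 30 per arm to 56% if 25 per arm remain.

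**The case against.** **Holds and reductions are prescribed, so they are not departures from the protocol.** This stands. Section 8.4.3 sets them out, and the PK-adjusted and tobramycin arms are adjusted to levels by design. A conventional per-protocol set would keep these subjects, so any second set has to be defined by exposure to the assigned regimen.

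**A reader might infer that these rules necessarily pull the arms together.** The documents do not show it. Arms converge only if the better arm loses more. If on-drug effects were equal and one arm stopped more often, the all-randomized difference would widen.

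**The size is a worst case.** This stands too. AKI incidence is not a rate of lost treatment: colistin is first held for a single dose and then restarted lower. The cohort difference is 3 points, not 5. Even undoing 15.5% dilution (the average of 12% and 19%) gives 3/0.845 ≈ 3.6, still inside the margin.

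**Dilution may not be complete.** The narrower intent-to-treat wording and the sentence on data before discontinuation could limit it. In part, yes, but the three-day rule still keeps anyone held, reduced or stopped later. Scheduled spirometry falls only at Visits 1 and 4, plus early termination, so data before a stop do not supply an on-regimen comparison.

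**Exposure is already reported.** Interruptions and total doses are secondary endpoints, so unequal exposure would be visible. They do not, however, test whether the equivalence result survives it.

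**Conclusion.** The gap is real and moderate in size. Equivalence is the primary FEV1 test, all randomized subjects form the only population defined for it, and nothing planned checks the result against exposure. Under the worst-case model the false-equivalence rate roughly doubles at an SD of 7 to 8. It rises to about 5-7% at SD 10 and stays near 2% at SD 11.6. These figures rest on an SD that the documents do not give, on full loss of effect in 12-19% of subjects, on a true difference exactly at the margin, and on a 90% interval.

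Two stronger readings are not supported. A reader might infer that equivalence will be declared too easily in this trial; at SD 10 or above with 30 per arm it is hard to declare even when true. A reader might also infer from the fixed-SD half-width at SD 11.6 (5.01, just above 5) that it could never be declared there. Allowing the sample SD to vary gives about 5% at a true difference of 0.

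**What to change.** Keep all randomized subjects as the primary set and change the following.

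1. In 15.2, add a pre-specified supportive equivalence analysis in an on-regimen set, defined from the doses recorded under 8.6: assigned drug and schedule, a pre-set share of the doses due under the protocol's own adjustment rules, no switch of study drug, and spirometry at Visits 1 and 4.
2. Reconcile the synopsis, 8.4.3 and 15.1 on which subjects form the efficacy population and on whether FEV1 measured after a stop is used.
3. State the unit of the margin and the interval level.
4. Report both intervals against ±5 points and qualify any equivalence claim if they disagree. Do not make the second set a formal gate.

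The cost is SAP wording and one extra run on data already collected. The downside is that the on-regimen set is smaller and leaves out subjects partly because of AKI, itself a primary safety outcome with historical rates that differ by drug. It loses some protection from randomization and power, which is why it should remain supportive.

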SUBJECT SELECTION CRITERIA: INCLUSION CRITERIA	CF patients 18 years or over who are diagnosed with APE based on CFF guidelines, and are chronically infected with P. aeruginosa , or other gram-negative bacteria, can produce sputum, undergo phlebotomy and provide written consent, will be eligible for participation, once their treating physician has determined that they should receive one of the two agents for APE treatment while hospitalized. Subjects able to receive either tobramycin or colistin as part of their IV antibiotic regimen will be randomized to one of three arms. If a treating physician deems that a subject cannot receive tobramycin due to vestibular or ototoxicity or bacterial resistance, the subject will be randomized to either standard or PK-adjusted colistin.

SUBJECT SELECTION CRITERIA: EXCLUSION CRITERIA	Presence of chronic renal insufficiency, with abnormal baseline creatinine >1.2.
TEST PRODUCT, DOSE, AND ROUTE OF ADMINISTRATION	Dosing of IV colistin will be determined based on serum concentrations of the drug on a BID dosing schedule.
CONTROL PRODUCT, DOSE AND ROUTE OF ADMINISTRATION	Dosing of IV tobramycin once daily will occur based on consensus guidelines and will be adjusted based on serum levels. Dosing of IV colistin TID will occur based on product insert (Perrigo Company).
STANDARD OF CARE TREATMENT	All study arms will be receiving APE treatment as a multi-drug therapeutic regimen, based upon CFF guidelines.
DURATION OF SUBJECT PARTICIPATION AND DURATION OF STUDY	Subjects will be on study for up to 14 days, or for the duration of their IV antibiotic treatment for APE while hospitalized. The study will enroll for 36 months.
CONCOMITANT MEDICATIONS	Allowed: Standard therapy for CF pulmonary exacerbations. Prohibited: none

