Safety analysis: The safety profile of each colistin arm and the tobramycin arm will be assessed in terms of the following: incidence of AKI, incidence of treatment related clinical events (ototoxicity, vestibular toxicity, and neurotoxicity). Adverse event rates will be compared between treatment groups using logistic regression, adjusting for age, medications such as vancomycin, baseline FEV₁, admits in the previous year, exposure to nephrotoxic antibiotics in the previous 5 years, and diagnosis of CF related diabetes (CFRD) as covariates. Repeated measures within subjects will be accounted for by including a random intercept for subjects.

Summary statistics and changes from admission will be presented for serum Cr and urine:protein ratios. The urine protein:creatinine ratio will be assessed as a biomarker of drug toxicity. We will analyze Nephrocheck® assay results in a case control design. Subjects who develop AKI within each of the study arms will have urine thawed and analyzed by Nephrocheck® and those results will be compared to age, gender, and FEV₁, matched control urines obtained from subjects

	within the study who did not develop AKI. An adjusted odds ratio will be derived from a model fitted with unconditional logistic regression and adjusted for confounding variables. Estimates of odds ratios and 99% confidence intervals will be presented.
RATIONALE FOR NUMBER OF SUBJECTS	In a retrospective cohort 500 subjects, FEV1% improvement after tobramycin treatment during exacerbation therapy was 3% higher than in those receiving colistin; however, rates of acute kidney injury (rise in serum creatinine ≥ 0.3 mg/dL while on therapy) were 60% higher in tobramycin treated subjects versus standard colistin treated subjects. Since no preliminary data was available on less frequent colistin dosing, which theoretically would lead to less frequent episodes of kidney injury, we estimate we are powered to identify a safer method for dosing colistin with samples of 30 subjects per group, though we may be underpowered to find a significant FEV ₁ difference between groups.

Title: IV Colistin for Pulmonary Exacerbations: Improving Safety and Efficacy

1. Background

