Colistimethate sodium or colistin, a member of the polymyxin family of antibiotics, is a powerful treatment option for APE, particularly with multi-drug resistant PA. While it has excellent antimicrobial activity against PA⁵, there has classically been a reluctance to use the drug due to its reported nephro- and neurotoxicity. More recent studies in ICU and CF populations suggest that nephrotoxicity secondary to colistin is less common than previously thought and is reversible. Studies comparing nephrotoxicity of intravenous colistin and aminoglycosides in CF actually demonstrate reduced toxicity with colistin^{3,6}. A major limitation to its use, however, is the lack of human *in vivo* data regarding its pharmacokinetics (PK) and pharmacodynamics (PD)⁷. There is no widespread consensus on best dosing intervals to optimize pathogen eradication and reduce renal toxicity; partly because the drug never underwent PK modeling studies prior to its FDA approval in the 1950s. Today, though colistin is frequently substituted for tobramycin during exacerbations in patients who have developed resistance to tobramycin, it is unclear how to dose the regimen for both safety and maximal efficacy—*i.e.* once daily versus three times daily, similar to questions posed with tobramycin prior to the TOPIC trial.

Currently, acute kidney injury (AKI), formerly known as acute renal failure, in CF is far greater than the background rate in the general population. In pediatric CF patients, AKI occurs at 100 times the general rate of AKI in children, and is primarily related to nephrotoxic antibiotic use⁸. In adults with chronic *Pseudomonas* airway infection, indices of renal impairment have been detected in 31-42% of the population⁵. Thus, the challenge remains to devise antimicrobial treatment strategies which are powerful enough to minimize antimicrobial resistance but also avoid longitudinal harm.

One limitation to improving safety of antimicrobial drug monitoring has been the lack of availability of clinical assays to measure levels of colistin from the serum. Highly accurate analytical techniques, now available through the University of Colorado School of Pharmacy, now make pharmacokinetic (PK) and pharmacodynamic (PD) studies of colistin possible in order to establish optimal dosing regimens for colistin. This technology

will allow optimization of colistin dosing in order to maximize efficacy and reduce toxicity associated with this agent.

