8. STUDY TREATMENTS

8.1 Method of assigning subjects to treatment groups

All subjects will enter the study at the time they are diagnosed with an APE and designated for hospital admission to treat with a drug regimen which includes either intravenous tobramycin or colistin. Block randomization will be utilized based on gender, FEV₁% predicted, and time of enrollment to ensure relatively equal treatment allocation based on these variables.

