8.3 Packaging and labeling of study drugs to site

Intravenous tobramycin (X-gen Pharmaceuticals) and intravenous colistin (Perrigo Company), which are administered to patients with CF APE, are purchased and formulated as solutions for intravenous administration by the Pharmacy Department at

National Jewish Health | Saint Joseph Hospital. There will be no change to the formulation or supplier of these products from current standard practice. The central study pharmacy is synonymous with National Jewish Health | Saint Joseph Hospital's inpatient pharmacy.

8.4 Handling and dosing regimens for study drugs.

8.4.1 Pre-treatment hydration: On the date of admission, all subjects will receive an initial normal saline (NS) 1 liter bolus. All subjects are initiated on the non-nephrotoxic component of their APE treatment on admission day one, as directed by their treating physician (beta lactam, carbapenem, monobactam, etc), based on infecting pathogen profile, previous treatment response, antimicrobial resistance, and drug allergies ³⁰⁻³². On the second hospital day, once a baseline serum creatinine (SCr) has been confirmed and the patients' attending physician and clinical pharmacist assess that they are ready to initiate treatment with either tobramycin or colistin, one of the three treatment arms will be implemented as directed by randomization. As per institutional protocol, all subjects receiving tobramycin or colistin receive 1 liter NS IV daily.

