9.3.2 Nephrotoxic Acute Kidney Injury assay (urine)

Urine will be obtained as noted in the Schedule of Events and will undergo cryopreservation. In patients who develop acute kidney injury (elevation of serum creatinine ≥ 0.3 mg/dL) urine will be thawed and evaluated for neutrophil gelatinase-associated lipocalin (NGAL) and tissue-inhibitor of metalloproteinase 2 (TIMP-2) and insulin-like growth factor binding protein 7 (IGFBP-7). NGAL will be evaluated by enzyme-linked immunosorbent assay (ELISA). TIMP-2 and IGFBP-7 will be measured by the Nephrocheck® assay. Nephrocheck® is a newly FDA approved assay for detection of nephrotoxic acute kidney injury and will be tested for its sensitivity and specificity for detection of acute kidney injury in CF within the study. Both assays will be run by the University of Colorado Renal Division.

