10 EVALUATIONS BY VISIT

10.1 Visit 1

1. Review the study with the subject (or subject's legal representative) and obtain written informed consent and HIPAA authorization.
2. Administer QoL questionnaire
3. Review respiratory culture results in the previous 12 months
4. Assign the subject a unique identification number.
5. Record demographics data.
6. Record medical history, including exacerbation criteria based on Rosenfeld score, baseline serum creatinine, and number of exacerbations in the preceding year.
7. Record concomitant medications.
8. Perform a complete physical examination.
9. Obtain and record vital signs.
10. Record oximetry.
11. Record results from blood and urine clinical laboratory tests (chemistry, hematology).

12. Record results from urine or blood pregnancy test (if female of child-bearing potential).
13. Record results from spirometry.
14. Record results from sputum culture microbiology.
15. Collect urine for Nephrocheck®

10.2 Visit 2

1. Administer QoL questionnaire
2. Record serum creatinine from daily clinical laboratory draws.
3. Collect urine for Nephrocheck®
4. Record urine protein from three times weekly clinical laboratory check.
5. Record tobramycin peak and trough from week 1 clinical laboratory draw
OR
Collect blood, sputum, and urine for colistin pk measurement.

10.3 Visit 3

1. Administer QoL questionnaire
2. Record serum creatinine from daily clinical laboratory draws.
3. Collect urine for Nephrocheck®
4. Record urine protein from three times weekly clinical laboratory check.
5. Record tobramycin peak and trough from week 2 clinical laboratory draw
OR
Collect blood, sputum, and urine for colistin pk measurement.

10.4 Visit 4

1. Administer QoL questionnaire.
2. Record concomitant medications.
3. Record spirometry.
4. Record serum creatinine from daily clinical laboratory draws.
5. Record results from sputum culture microbiology.
6. Record total number of IV antibiotics doses over the preceding 14 days.
7. Collect urine sample for Nephrocheck®.
8. Complete Case Report Form (for toxicities).

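### The AKI model omits baseline serum creatinine, a recorded value arithmetically tied to the 0.3 mg/dL threshold; adding it is cheap, and the likely effect is modest

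*Combined protocol and SAP*

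**What the plan says.** The synopsis and section 15.3 give one covariate list for all adverse event rates: "adjusting for age, medications such as vancomycin, baseline FEV₁, admits in the previous year, exposure to nephrotoxic antibiotics in the previous 5 years", plus CF-related diabetes. That makes six covariates, none of them a measure of renal function.

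The value is available. Visit 1 (section 10.1, item 6) reads "Record medical history, including exacerbation criteria based on Rosenfeld score, baseline serum creatinine, and number of exacerbations in the preceding year". Section 8.4.1 starts tobramycin or colistin on the second hospital day, "once a baseline serum creatinine (SCr) has been confirmed".

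The design does not balance it. Section 8.1 says "Block randomization will be utilized based on gender", followed by FEV1 % predicted and time of enrolment. The exclusion criterion does limit the upper end: "Presence of chronic renal insufficiency, with abnormal baseline creatinine >1.2" mg/dL.

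On the endpoint, section 9.3.2 says "In patients who develop acute kidney injury (elevation of serum creatinine ≥ 0.3 mg/dL", and the retrospective cohort in section 1.1 and the sample size text in 15.4 use the same threshold. The primary endpoint itself (5.1) cites KDIGO criteria without writing out thresholds.

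Section 15.3 promises summary statistics and changes from admission for creatinine. The baseline characteristics listed in 15.1 do not include it.

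**The concern.** AKI is part of the primary safety endpoints, and section 15.4 rests the choice of 30 per group on it. With a fixed absolute threshold, two subjects with the same proportional loss of renal function can be classified differently only because they started from different creatinine values. No listed covariate is tied to the endpoint in this way. If the arms differ at baseline, part of that difference can pass into the AKI odds ratio, and the planned model has no term to remove it.

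Chance is not the only route. A subject who cannot receive tobramycin is randomised between the two colistin arms only (6.2, item 6). Section 2.1 lets a subject who cannot receive colistin enter the tobramycin arm only. For tobramycin versus colistin, the arms are therefore not formed wholly by randomisation.

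**Working it through.** **The plan's own figures.** Section 1.1 gives AKI of 19% on tobramycin and 12% on colistin. The ratio is 0.19/0.12 = 1.58, which agrees with the 60% excess in 15.4. The crude odds ratio is (0.19/0.81)/(0.12/0.88) = 1.72. The cohort's reported odds ratio of 3.6 comes from an analysis adjusted for prior-year admissions.

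**Relative rise needed to reach 0.3 mg/dL.**
- From 0.5 mg/dL: 0.3/0.5 = 60%
- From 0.77 (pilot mean, Table 1): 0.3/0.77 = 39%
- From 1.2 (eligibility ceiling): 0.3/1.2 = 25%

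**Strength of the link.** The documents give no data relating baseline creatinine to a 0.3 rise, so this step is modelled. Baseline is normal with the pilot's mean 0.77 and SD 0.27 (n = 16), cut at 1.2. Overall AKI is set at 12%. Two forms were used, both assuming that the proportional change does not depend on baseline:
- peak/baseline ratio lognormal, log-SD 0.15 to 0.30: AKI risk 2–5% at 0.5 mg/dL and 21–31% at 1.2;
- proportional rise lognormal, log-SD 0.6 to 1.0, baseline floor 0.4: risk 2–5% at 0.5 and 23–30% at 1.2.

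The odds ratio per SD of baseline is about 1.6 to 2.5. It falls to about 1.4 to 2.1 if a 1.5-times-baseline criterion (assumed here) also counts as AKI. In the second form, with overall AKI at 12% or 19%, the AUC is 0.63–0.71 and the variance explained is 2–7%. If instead the absolute rise is independent of baseline, the odds ratio is 1.0.

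**Effect of chance imbalance.** The SE of the difference in means between two arms of 30 is √(2/30) = 0.258 SD. That is 0.070 mg/dL at SD 0.27, or 0.051 at the truncated SD of 0.20. The shift in the odds ratio is (OR per SD)^0.258:
- 1.4^0.258 = 1.09
- 2.5^0.258 = 1.27
- at 1.0 there is no shift

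**Sampling error for comparison.** Expected events are 30 × 0.19 = 5.7 and 30 × 0.12 = 3.6.

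SE(log OR) = √(1/5.7 + 1/24.3 + 1/3.6 + 1/26.4) = 0.73

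One SE is a factor of e^0.73 ≈ 2.1. The imbalance shift is ln 1.09/0.73 = 12% to ln 1.27/0.73 = 33% of that.

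On the risk scale, with no drug effect, the second form gives an imbalance-driven shift with SD 1.3–2.7 points and a 97.5th percentile of 2.5–5.3 points. The sampling SE is 8.4–10.1 points, and the difference of interest is 7 points.

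**False positives.** In simulated trials with no drug effect, Wald logistic tests rejected in 1.2–3.5% without baseline creatinine and 1.6–4.0% with it. Under penalised logistic regression the figures were 4.6% and 5.0%.

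**Room in the model.** With 6–12% AKI assumed in the PK-adjusted arm, total events are 5.7 + 3.6 + 1.8 to 3.6 = 11.1 to 12.9. Six covariates plus two arm terms make 8 parameters, more if other medication needs several terms. That is 1.4–1.6 events per parameter, falling to 1.2–1.4 with a ninth.

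**The case against.** The strongest objection is that this is a covariate preference with little effect on inference. Chance imbalance under randomisation is already inside the test's error rate, and the simulations confirm that adjustment does not lower it. The power gain is small: 71% to 73% in a simulation of 12% versus 40% AKI, where the 40% is not a figure from the documents. The whole effect rests on the proportional rise being independent of baseline. Error in the measured baseline works the other way, since a falsely low baseline makes a 0.3 rise easier to reach. The 1.2 ceiling narrows the range, age, CF-related diabetes and five-year nephrotoxic exposure may carry some of the same information, and 15.3 already promises creatinine summaries. Low power at 30 per arm matters far more: about 11% two-sided for 19% versus 12%.

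All of this stands as a limit on the size of the point. It does not show that a recorded baseline value tied to the endpoint should stay out of the model.

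A reader might also infer that baseline creatinine largely decides who reaches AKI. The documents contain no evidence for this, and the modelled AUC of 0.63–0.71 is that of a moderate predictor. The Background statement that "indices of renal impairment have been detected in 31-42% of the population" concerns adults with chronic Pseudomonas infection generally, not this trial's population after its creatinine exclusion. A reader might likewise suppose that prior-year admissions could be dropped because it duplicates five-year exposure. Nothing supports that overlap, and the sponsor's own retrospective AKI analysis adjusted for prior-year admissions.

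**Conclusion.** The omission is real and appears in both places where the model is described. It is minor. Under the proportional-rise assumption, a one-SE chance imbalance moves the AKI odds ratio by a factor of about 1.1 to 1.27. This falls to 1.0 if the absolute rise does not depend on baseline, and it is small beside a sampling factor of about 2.1. These figures rest on a 16-patient pilot distribution and on assumed response models.

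Adjustment would reduce bias in the comparison actually observed. It would not reduce overall type I error. The reason is stronger for tobramycin versus colistin, where restricted eligibility could make imbalance systematic. The documents do not show that the restricted subjects differ in renal function, so this is a possibility and not a finding. For standard versus PK-adjusted colistin, only chance imbalance applies.

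**What to change.** In section 15.3 and the synopsis, pre-specify serum creatinine as a continuous covariate in the AKI model. Define it as the last value before the first dose of study drug, because the Visit 1 value and the one confirmed on hospital day 2, after the admission saline bolus, need not agree. Add baseline creatinine by arm to the baseline table.

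With about 11–13 expected AKI events for 8 or more parameters, fit the AKI model with a penalised (Firth) likelihood or a short covariate set fixed in advance. Do not remove prior-year admissions on the ground that it overlaps five-year exposure. Write out the KDIGO thresholds used for the endpoint, since the strength of the link depends on them.

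The cost is a few lines of text and no new data. AKI would need its own model statement, because the present list serves all adverse events. The drawback is one more term in an already sparse model, with little gain in power.
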